# Neuromodulation for Children with Cystic Fibrosis

## Experiencing Chronic Abdominal Pain

NCT05515250

Last review date 07/25/2023

**STUDY PROTOCOL:** Eligible participants will be recruited from the gastroenterology or Cystic Fibrosis clinics at Cardinal Glennon Hospital, Saint Louis University and Saint Louis Children's Hospital at Washington University in Saint Louis. Consent to participate and a detailed history, physical examination and laboratory tests for stool calprotectin will be obtained at the participants' clinical management site. A global assessment of abdominal pain will be used to rate its severity. Participants will be allowed to continue medication regimens that they are on prior to enrollment. No adjustments in medications will be allowed during the 3-week study period unless deemed necessary by the CF care team. Also, no new medications or OTC treatments will be allowed during the 3-weeks trial of PENFS unless deemed necessary by the CF care team. The use of all medications will be carefully monitored each week for future evaluation.

Following screening evaluation, enrolled participants will complete questionnaires and have the initial PENFS device placed by a trained health care professional. Device placement will then be done at the gastroenterology clinic at Cardinal Glennon Hospital to which participants will return every 7 days for a total of 3 visits for device replacement and completion of questionnaires. Three different devices will be placed in total (at baseline, at the end of week 1, and at the end of week 2). Following each visit and at week 8, participants will complete follow-up pain, CFQ-R, IBS-SSS, and PedsQL GI symptom scale administered in person by the study clinical coordinator at the clinical management site. The PI and sub-investigators at each clinical site will review adverse events on a continual basis to watch for unexpected safety signals.

Table 1 presents the expected timeline. The total length of the study, from screening of the first participant to the end of the study, is expected to be approximately 12 months

	Screening/ baseline	End of Week 1	End of Week 2	End of Week 4 **	8-week follow- up **
Informed Consent/enrollment	X				
Eligibility assessment	X				
Demography and Medical history	X				
Check Current Medication	X	X	X	X	X
IB-Stim Placement	X	X	X		
Pain Score*	X	X	X	X	X
CFQ-R*	X	X	X	X	X
IBS-SSS*	X	X	X	X	X
PedsQL GI symptom scale Version 3.0*	X	X	X	X	X
Stool Calprotectin	X a			X b	

**STATISTICAL PLAN**(in conjunction with the AHEAD Institute at St. Louis University): The primary endpoint for this study is the change in the abdominal pain scores from baseline to study exit. The secondary endpoints will be the change in the IBS-SSS (Symptoms Severity Scale), CFQ-R, and PedsQL Gastrointestinal symptom scale from baseline to study exit. The median pain scores will be computed at the three time points in the study (baseline, at 4 weeks and at 8 weeks) and compared using the non-parametric Kruskal Wallis test. Ad-hoc pairwise comparisons will be done using the Dwass, Steel, Critchlow-Fligner multiple comparison procedure (10,11). Trends in these indices over time will be compared using mixed models adjusting for repeated measures. These statistics will also be computed for the secondary endpoints. REDCap (Research Electronic Data Capture), a secure web-based application or password protected excel, will be used for data management and storage. P-values < 0.05 are considered significant. All analysis will be two-sided and completed in SAS 9.4 or the current version of SAS at the time of the study (SAS Institute Inc., Cary, NC, USA).

Due to less-than-optimal numbers of participants, this study was closed after enrolling one patient. Therefore, the above statistical methods could not be applied.

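### Does it call for a change that medication limits end with the 3-week device period while the pain scores compared come at weeks 4 and 8, with no analysis role for the medication records?

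*Combined protocol and SAP*

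**What the plan says.** The Study Protocol section lets participants stay on the regimens they had before enrolment and sets two limits. The first is "No adjustments in medications will be allowed during the 3-week study period unless deemed necessary by the CF care team". The second is that "no new medications or OTC treatments will be allowed during the 3-weeks trial of PENFS unless deemed necessary by the CF care team". The length of the period follows from the device schedule: "Three different devices will be placed in total (at baseline, at the end of week 1, and at the end of week 2", with returns every 7 days.

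On records, the same section says: "The use of all medications will be carefully monitored each week for future evaluation". In Table 1 the row "Check Current Medication" is marked in all five columns: baseline and weeks 1, 2, 4 and 8. The pain score row is marked in the same five columns.

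The Statistical Plan states: "The primary endpoint for this study is the change in the abdominal pain scores from baseline to study exit". For the main comparison, "The median pain scores will be computed at the three time points in the study (baseline, at 4 weeks and at 8 weeks", by a Kruskal-Wallis test with pairwise follow-up. It adds: "Trends in these indices over time will be compared using mixed models adjusting for repeated measures". Medication is not mentioned there as a count, a model term, a sensitivity analysis or a handling rule. The section ends by reporting closure after one enrolled patient, with the planned methods not applied.

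**The concern.** The limits and the analysis refer to different stretches of time. The scores taken while the limits apply (weeks 1 and 2) are not in the named median comparison. Both follow-up scores that are in it come when no limit is stated in the visible text. Even inside the three weeks, the care team may make exceptions.

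With no comparator described, a fall in pain after a new drug is started looks the same as a fall due to the device. Added treatment would flatter the device; reduced treatment would work against it. The protocol treats medication as worth restricting and recording, yet its statistical section leaves the records without a stated use. A reader could fairly fear that the handling would be chosen after the scores were seen.

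Two drafting points sit beside this. Study exit is not tied to a visit, and the text speaks of weekly medication monitoring while Table 1 has no check at week 3 or between weeks 4 and 8.

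**Working it through.** The documents give no rate of medication change, no drug effect and no range for the pain scale, so there is no figure of the plan's own to reproduce. What can be checked is the timing, the overlap of records and scores, and what an adjustment would achieve.

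**Timing** (device schedule and visit interval from Study Protocol; time points from Statistical Plan)
- End of device period: 3 devices × 7 days = about day 21. The documents imply this day but do not state it.
- Week 4: 28 − 21 = about 7 days after the limits end.
- Week 8: 56 − 21 = about 35 days after.
- So 2 of the 2 follow-up points in the median comparison fall outside the limits. The mixed models may also use weeks 1 and 2, since their time points are not listed.

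**Records against scores** (Table 1)
- Pain score: baseline, weeks 1, 2, 4, 8. Medication check: the same 5 visits.
- Of these, 4 are post-baseline and can show a change since the previous check. The longest gap is 8 − 4 = 4 weeks.
- Every analysed score therefore has a medication record from the same visit.

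**Possible size, on assumed values only.** Let *p* be the share of children with a changed drug at a visit and *d* the drug's effect in SDs of the change score.
- Shift in mean change = *p* × *d*.
- Smallest: 0.10 × 0.5 = 0.05 SD. Largest: 0.30 × 1.0 = 0.30 SD.
- Shift in the median, assuming normal scores, solves (1 − *p*)F(*x*) + *p*F(*x* + *d*) = 0.5, where F is the standard normal distribution function and the shift is the size of *x*. It runs from 0.049 to 0.286 SD.
- For new or increased drugs the shift favours the device. For reduced or stopped drugs of the same share and effect it has the same size and the opposite sign. With equal shares the shift in the mean is *p* × *d* − *p* × *d* = 0.
- Nothing in the documents says which direction would prevail.

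**What an adjustment would do.** The natural candidate sets a score taken on an added drug to the worse of baseline and observed.
- Take higher scores as worse, with baseline *B* and observed score *Y*. The replacement is *Y\** = max(*B*, *Y*) ≥ *Y*, so *Y\** − *B* ≥ *Y* − *B* for every child affected.
- Its direction is thus fixed before any data are seen, and reduced medication has no counterpart in it.
- It needs a drug list and a look-back window, neither of which the documents supply. The window matters. For a listed course on days 1 to 5 and visits on days 7, 14, 28 and 56, windows of 0, 7 or 14 days overwrite 0, 1 or 2 of the 4 scores. With no time limit, all 4 are overwritten.
- Imputed scores can make standard errors too small. If run only in the mixed model, the rule leaves the Kruskal-Wallis comparison untouched.

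**The two drafting points**
- Study exit: week 8 is the last visit in Table 1 and is the natural reading. If week 4 were meant instead, the pairwise comparisons already cover baseline against each of the two.
- Weekly monitoring: Table 1 is the operative visit schedule, and the text is a loose description of it.

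**The case for a change.** The strongest case for a change is about pre-specification. Recording data for later use states a purpose but no method, and choosing the handling after seeing the scores is what a plan should prevent. Medication also differs from the other confounders in an uncontrolled study, because here the data are already collected. A table of counts would cost almost nothing and would let a reader judge how much of the change drugs might explain.

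Much of this stands. The gap is real, and a report without such counts would be weaker. But a count of children with new or increased, and with reduced or stopped, medication at each visit is ordinary reporting that a competent analyst would produce from the existing checks. It is descriptive and offers little room for selective choice. The part that would need firm advance rules is a formal adjustment, and that part brings no clear gain.

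Using scores as observed, whatever is taken during follow-up, is also a legitimate choice for a small uncontrolled study. Limiting changes during treatment and recording them afterwards is a coherent design.

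**Conclusion.** The description of the plan is right, but no change follows. The statistical section omits a detail that analysts can fill sensibly: report medication changes by visit beside the as-observed pain scores, take the last scheduled visit as study exit, and follow Table 1 for the checks. A further analysis would not make change from baseline attributable to the device, because natural course, regression to the mean and placebo response stay unseparated whatever is done about drugs.

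The size of any bias is unknown. The 0.05 to 0.30 SD range rests wholly on assumed shares (10% to 30%) and effects (0.5 to 1.0 SD), could take either sign, and carries no weight in this conclusion. For this study the practical effect on results is nil: one patient was enrolled and the methods were not applied.

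The conclusion assumes that the period ends at about day 21 and that the table notes do not alter the schedule. The notes marked on the week 4 and week 8 columns are not visible in the text available, so nothing is inferred from them. The clinical medication rule itself is not in question here.

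### The primary endpoint is a single baseline-to-exit change, but the lead test compares three time points, exit is tied to no visit, and no test is named as deciding

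*Combined protocol and SAP*

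**What the plan says.** The relevant text is all in the Statistical Plan section of the combined protocol and SAP.

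- Endpoint: "The primary endpoint for this study is the change in the abdominal pain scores from baseline to study exit".
- First analysis: "The median pain scores will be computed at the three time points in the study (baseline, at 4 weeks and at 8 weeks"), and these are to be "compared using the non-parametric Kruskal Wallis test".
- Second: "Ad-hoc pairwise comparisons will be done using the Dwass, Steel, Critchlow-Fligner multiple comparison procedure".
- Third: "Trends in these indices over time will be compared using mixed models adjusting for repeated measures".
- Threshold: "P-values < 0.05 are considered significant". It applies to every analysis alike.
- Secondary outcomes: "These statistics will also be computed for the secondary endpoints".

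No sentence says which visit is the exit. The Study Protocol section describes a study period of three weeks, while Table 1 has visits at the end of week 4 and at week 8, the latter labelled follow-up. Table 1 schedules pain scores at five visits, and the plan does not say which of them enter the mixed model. The section ends by reporting that "this study was closed after enrolling one patient" and that the planned methods could not be applied.

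**The concern.** The endpoint is a within-child difference between two times. The lead test asks whether any of three times differs from the others. It can reject, correctly, because week 4 alone differs, and that is not a change from baseline to week 8. If exit means week 4, the reverse holds: a change that appears only at week 8 can make the test significant.

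Kruskal-Wallis and the pairwise procedure also treat repeated scores from the same children as independent samples, which wastes power for the contrast that the endpoint names. Three analyses share one threshold with no order among them, so they can answer the primary question differently and the plan does not say which answer counts. The secondary endpoints inherit the same structure.

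**Working it through.** **Inputs from the documents.** Three time points (weeks 0, 4 and 8), Kruskal-Wallis, Dwass-Steel-Critchlow-Fligner (DSCF) pairs, a repeated-measures trend model, and two-sided 0.05. There is no sample size, SD, effect size or power figure, so there is no figure of the plan's own to reproduce.

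**Assumptions.** n = 10 to 30 children, SD 1, equal within-child correlation ρ = 0.3 to 0.7, complete normal data, 10,000 simulated trials per setting. Exit is taken as week 8 except in step 5.

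**1. What each analysis tests.** Kruskal-Wallis has 3 − 1 = 2 degrees of freedom and rejects for any difference among the three visits. DSCF covers three pairs, of which baseline versus week 8 is one. For the trend, centre the times at −4, 0, 4. With complete data and a random intercept, the slope is

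[4 × (mean at week 8) − 4 × (mean at baseline)] / (16 + 0 + 16) = (week 8 − baseline) / 8.

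If fitted to weeks 0, 4 and 8, the trend therefore estimates the week-8 change; only the residual variance and its degrees of freedom differ from those of a model with categorical visits.

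**2. Change at week 4 only** (means 0, −0.6, 0; the week-8 change is zero). Share of trials significant, over ρ = 0.3 to 0.7:

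| n | Kruskal-Wallis |
|---|---|
| 10 | 9-16% |
| 20 | 34-40% |
| 30 | 62-63% |

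Over all these settings the DSCF baseline-week-8 pair is significant in at most 0.7%, the trend in 2-4%, and a categorical-visit week-8 contrast in about 5%.

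**3. True week-8 change** of 0.6 SD, n = 20, ρ = 0.5. By hand for the contrast: the SD of a within-child difference is √[2(1 − 0.5)] = 1, the standard error is 1/√20 = 0.224, and the noncentrality is 0.6/0.224 = 2.68. With 2 × (20 − 1) = 38 degrees of freedom the critical value is 2.02 and power is about 74%. Simulation, with week 4 either unchanged or also at −0.6:

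| Analysis | Power |
|---|---|
| Kruskal-Wallis | 36-37% |
| DSCF baseline-week-8 pair | 22% |
| Trend (weeks 0, 4, 8) | 72-73% |
| Categorical-visit contrast | 74-75% |

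Kruskal-Wallis, the pair and the trend do not all agree in 53-54% of these trials, and in 28-73% over the full range of n and ρ.

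**4. No change at any visit.** At least one of the written tests is significant in 4.8-6.4% of trials.

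**5. If exit is week 4.** A separate simulation (1,500 trials per setting, ρ = 0 to 0.7) used means 0, 0, −0.5, so that the baseline-to-week-4 change is zero. Kruskal-Wallis was significant in 18-33% at n = 20 and 58-60% at n = 40. By the formula in step 1, the trend would then also be estimating the change to the wrong visit.

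**The case against.** Five points can be made for the plan.

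- *Any omnibus test behaves this way, and the pairs are there to sort it out.* The pairs do include baseline versus week 8, which rarely misleads in step 2. But they are called ad-hoc, none is designated, and that pair has 22% power where the paired contrast has 74-75%.
- *The mixed model already supplies the contrast.* This is the strongest point. On weeks 0, 4 and 8 its slope is the week-8 change divided by 8, so the correction adds almost no power over the trend. It holds only if exit is week 8 and the model uses those three visits, and the plan states neither, nor that the model decides. Much of the disagreement in step 3 comes from setting unpaired tests beside a paired one; it shows that the choice of test matters, not how often exit would be misread.
- *Error is not inflated.* Correct. DSCF adjusts across its three pairs, and the overall rate stays near 5%.
- *The percentages rest on assumed values and on normal data, while pain scores are bounded.* The first part stands. On the second, a repeat with rounded scores limited to 0-10 gave the same pattern. The logical mismatch needs none of these assumptions.
- *The study closed after one patient.* True, and no reported result is affected. Low enrolment explains why the methods were not used; it does not repair them.

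The double asterisks on weeks 4 and 8 in Table 1 have no visible footnote, so some text may have been lost. A footnote defining exit would settle the visit, but not the mismatch between an omnibus test and a single contrast.

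**Conclusion.** The concern holds. The endpoint names one contrast; the lead test does not isolate it and ignores the pairing; exit is undefined, although week 8, the last scheduled visit, is the natural reading; and no analysis is named as deciding. The harm is to interpretation and power, not to the false-positive rate. Under the stated assumptions, the lead test is significant in 9-63% of trials when only week 4 changes, and it has about half the power of the direct contrast for a real week-8 change at n = 20 and ρ = 0.5 (36-37% against 74-75%). These sizes move with the assumed n, correlation and mean profile. With one patient enrolled and no test run, this is a correction that should be made if the plan is reused, not one that changes any reported finding.

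**What to change.** Before any analysis under a reused plan, the sponsor ties *study exit* to one visit (the 8-week follow-up is the natural reading) and adds a sentence such as:

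> The primary analysis is the exit-visit-minus-baseline contrast in pain score from a repeated-measures mixed model with visit as a categorical factor, two-sided 0.05.

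The text should also state which visits enter the model, the covariance structure and the degrees-of-freedom method, since these matter in a small trial. The other follow-up visit, the omnibus test, the pairwise comparisons and the trend are labelled supportive. The same contrast is used for the secondary endpoints.

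The cost is SAP wording only; no visit or measurement changes. There are two drawbacks. The visit not chosen as exit can no longer be reported as the primary result. The model also assumes roughly normal errors and scores missing at random, in return for using all available visits when an exit score is missing.

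### The primary endpoint is a within-child change, but the plan names only visit medians and p-values, with no baseline-to-exit estimate or confidence interval to report

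*Combined protocol and SAP*

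**What the plan says.** All of the relevant text is in the STATISTICAL PLAN section of the combined protocol and SAP.

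- **Endpoint:** "The primary endpoint for this study is the change in the abdominal pain scores from baseline to study exit".
- **Summary:** "The median pain scores will be computed at the three time points in the study". The time points are baseline, week 4 and week 8.
- **Comparison of the medians:** "compared using the non-parametric Kruskal Wallis test".
- **Pairwise follow-up:** "Ad-hoc pairwise comparisons will be done using the Dwass, Steel, Critchlow-Fligner multiple comparison procedure".
- **Longitudinal analysis:** "Trends in these indices over time will be compared using mixed models adjusting for repeated measures".
- **Secondary endpoints:** "These statistics will also be computed for the secondary endpoints". This covers IBS-SSS, CFQ-R and the PedsQL gastrointestinal scale.
- **Decision rule:** "P-values < 0.05 are considered significant", two-sided.

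The section mentions no mean or median change, no paired estimate and no confidence interval. It does not say which visit is study exit; the last column of Table 1 is the 8-week follow-up. It closes by stating that enrolment stopped at one patient and that the methods could not be used.

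**The concern.** The endpoint is defined within a child: exit score minus baseline score. The named summary is a property of each visit taken separately. Subtracting one visit median from another does not give the median of the children's changes, and it makes no use of the fact that the same children were measured each time. This is a mismatch between endpoint and summary. It would remain even if the independent-groups tests were replaced by a paired test.

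The protocol describes no comparison arm, so the size of the change and its uncertainty would be the main usable result. Three medians and a p-value cannot show whether a non-significant result excludes a worthwhile fall in pain, or how large a significant fall is. Because the same statistics are applied to the secondary endpoints, the gap covers all four endpoints.

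**Working it through.** **Inputs.** The documents give no sample size, SD, score range or within-child correlation, so there is no figure of the plan's own to reproduce. Every numerical input below is an assumption. The calculations answer one conditional question: what happens if the difference between visit medians is taken as the effect?

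**1. Can the two summaries disagree?** Constructed data for five children:

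| Child | Baseline | Exit | Change |
|---|---|---|---|
| 1 | 4 | 2 | -2 |
| 2 | 5 | 3 | -2 |
| 3 | 6 | 7 | +1 |
| 4 | 8 | 6 | -2 |
| 5 | 9 | 7 | -2 |

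- Baseline median 6; exit median (2, 3, 6, 7, 7) 6; difference of medians 0.
- Median change -2, with four of five children improved.
- Hodges-Lehmann estimate: of the 15 pairwise (Walsh) averages, 10 equal -2, four equal -0.5 and one equals +1. Their median, the 8th, is -2.

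A second constructed set has baseline 2, 3, 5, 6, 7 and exit 1, 2, 6, 5, 6, each pair repeated four times (n = 20). Both visit medians are 5, although 16 of 20 children improve. The median change is -1 and the mean change -0.6 (95% CI -0.98 to -0.22). Kruskal-Wallis on the two visits gives p = 0.27; Wilcoxon signed-rank gives p = 0.007.

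**2. How much precision is lost?** Assume bivariate normal scores with equal variance σ² and correlation ρ. Large-sample variances, multiplied by n/σ²:

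- Difference of visit medians: 2(π/2 − arcsin ρ)
- Hodges-Lehmann estimate of the paired change: 2(1 − ρ)π/3

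| ρ | Difference of medians | Hodges-Lehmann | Efficiency (ratio) |
|---|---|---|---|
| 0.3 | 2.53 | 1.47 | 0.58 |
| 0.5 | 2.09 | 1.05 | 0.50 |
| 0.7 | 1.59 | 0.63 | 0.39 |

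In 20,000 simulated trials per setting, the efficiency was 0.70, 0.63 and 0.53 at n = 10, and 0.63, 0.55 and 0.46 at n = 20. At n = 10 the standard error is therefore larger by a factor of 1/√0.70 = 1.20 to 1/√0.53 = 1.37.

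**3. How often does the sign mislead?** A separate simulation used 4,000 runs per setting, integer scores from 0 to 10, SD 2, mean 6 at baseline and 5 at exit, n = 10, 20 or 30, and correlation 0.3 to 0.9. Among runs in which more than half the children improved, the difference of medians was zero or in the wrong direction in about 5% to 9%. It also varied more than the mean within-child change:

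| n | Correlation | SD, difference of medians | SD, mean change |
|---|---|---|---|
| 10 | 0.3 | 0.98 | 0.73 |
| 20 | 0.5 | 0.70 | 0.46 |
| 30 | 0.9 | 0.43 | 0.17 |

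**The case against.** The strongest reply is the mixed-model sentence. A reader might infer from the visit medians that the plan has no within-child analysis at all. The documents do not support that: repeated-measures mixed models are planned for pain and for the secondary endpoints, they use each child's own data, and they could yield an estimated mean change with an interval. What remains is narrower. The sentence is about trends, and it names no baseline-to-exit contrast and nothing to be reported. A model able to produce the estimate is not a commitment to report it.

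Second, a reader might infer that the plan adopts the difference between visit medians as its effect estimate. It does not say so. The efficiency figures therefore describe what follows if the medians are read that way, and they depend on an assumed distribution, correlation and sample size. The five-child data were built to give a zero, and under the model simulated that outcome was uncommon.

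Third, a missing interval leaves precision unreported; it does not make an estimate imprecise. The precision loss comes only from using unpaired medians.

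Fourth, part of the force belongs to a separate problem, the use of independent-groups tests on repeated visits. That stands, but changing the test alone would not supply an estimate or an interval.

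**Conclusion.** The concern holds as a gap in the plan. The endpoint is a within-child change, the named summary is a set of visit medians judged by p-value, and no estimate or interval for the change is specified for any of the four endpoints.

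If the difference of medians were taken as the effect, its large-sample efficiency would be about 58% to 39% of that of the paired Hodges-Lehmann estimate, under bivariate normality with correlation 0.3 to 0.7. At an assumed n = 10 it would be about 70% to 53%. A zero or wrong-direction value when most children improve is possible but not typical, at about 5% to 9% under one assumed model.

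A reader might also infer that a published effect is misleading. The documents rule that out: one patient was enrolled and the methods were not applied. With one child, neither the plan nor the fix gives an interval. The practical weight is low unless the plan is reopened or reused.

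**What to change.** Replace the sentence on visit medians with wording such as: *The effect is the within-child change in pain from baseline to study exit (week 8), reported with a 95% confidence interval. The same is reported for week 4 and for each secondary endpoint. Visit medians and quartiles are descriptive.*

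Three details need settling in advance:

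1. **Exit visit.** Week 8 is the last visit in Table 1, but the sponsor must confirm that it is study exit.
2. **One primary method.** Use either the Hodges-Lehmann paired estimate or a named baseline-to-exit contrast from the mixed model already planned. The contrast is the smaller change to the plan.
3. **Very small numbers.** State that the exact coverage attained will be reported. For the signed-rank interval at n = 5 it is at most 1 − 2/2⁵ = 93.75%, so a full 95% interval is not available.

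The cost is one paragraph of SAP wording and slightly more analysis work. It needs no new data, visits or patients.

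### The specified comparison treats three of five collected visits as independent groups, leaves weeks 1 and 2 without a stated role, and has no missing-data rule

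*Combined protocol and SAP*

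**What the plan says.** In the study protocol section, Table 1 marks the pain score, CFQ-R, IBS-SSS and PedsQL GI scale at all five visits. The narrative agrees that scores are taken repeatedly: "Following each visit and at week 8, participants will complete follow-up pain, CFQ-R, IBS-SSS, and PedsQL GI symptom scale". On treatment timing it says "Three different devices will be placed in total (at baseline, at the end of week 1, and at the end of week 2"), and it calls the treatment period the "no new medications or OTC treatments will be allowed during the 3-weeks trial of PENFS" window, that is, three weeks.

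The Statistical Plan defines the endpoint: "The primary endpoint for this study is the change in the abdominal pain scores from baseline to study exit". It does not say whether exit is week 4 or week 8. For the analysis it states "The median pain scores will be computed at the three time points in the study (baseline, at 4 weeks and at 8 weeks"), to be "compared using the non-parametric Kruskal Wallis test", with Dwass-Steel-Critchlow-Fligner pairwise comparisons. It then adds "Trends in these indices over time will be compared using mixed models adjusting for repeated measures". The same statistics apply to the secondary endpoints. No analysis set, expected dropout or rule for missing scores is given. The plan closes by noting that the study stopped after one patient and that the methods could not be applied.

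**The concern.** The schedule has five visits, but the only comparison whose visits are named has three, which the plan describes as the time points of the study. The two visits left out are the ones inside the device period. They are also the scores most likely to be on record before a child stops attending.

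The chosen tests treat visits as separate groups. With nothing said about missing scores, each median by default summarises the children who have a score at that visit. If attendance is related to pain, the difference between medians mixes a change within children with a change in who is counted. A mixed model can correct for this when dropout depends on scores that the model contains. Whether weeks 1 and 2 are in the planned model is therefore important, and the plan does not say.

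**Working it through.** **1. Visits side by side**

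| Visit | Scores collected (Table 1) | In the named comparison | Timing against devices |
|---|---|---|---|
| Baseline | yes | yes | first device placed |
| Week 1 (day 7) | yes | no | device period |
| Week 2 (day 14) | yes | no | device period |
| Week 4 (day 28) | yes | yes | after |
| Week 8 (day 56) | yes | yes | after |

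Three devices at 7-day intervals cover 3 × 7 = 21 days, so week 4 falls 28 − 21 = 7 days after treatment. The comparison uses 3 of 5 visits and omits 2 of 4 post-baseline visits, both of them on treatment.

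**2. Inputs for size.** The documents give no SD, correlation, dropout rate, effect or planned sample size, so there is no figure of theirs to reproduce. Everything below is assumed: no true change, SD 2 points, equal correlation ρ = 0.5 between visits, 30% lost by week 8 (half of them by week 4). The children lost are those with the highest week 2 pain plus random noise of SD 1.

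**3. Hand calculation.** This treats the loss as one step. Let δ be the mean week 2 shift, in SD, among those who stay. The mean of the lower 70% of a standard normal is −φ(0.524)/0.70 = −0.348/0.70 = −0.497. The correlation of week 2 pain with the dropout score is 2/√(2² + 1²) = 0.894. So δ = −0.497 × 0.894 = −0.444.

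- Available-case shift at week 8: ρδ = 0.5 × −0.444 = −0.222 SD, or −0.44 points.
- Mixed model without weeks 1 and 2: the stayers' baseline is also shifted by ρδ, so the model explains ρ²δ and leaves ρ(1 − ρ)δ = 0.25 × −0.444 = −0.111 SD, or −0.22 points.
- Mixed model with week 2: dropout depends only on a score in the model, which leaves 0.

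**4. Simulation (4,000 children, same assumptions), week 8 minus baseline in points; the true value is 0**

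| Who leaves | Available-case medians | Three-visit model | Five-visit model | Paired completers (mean) |
|---|---|---|---|---|
| High recorded week 2 pain | −0.44 | −0.21 | −0.01 | 0.01 |
| Low recorded week 2 pain | 0.46 | 0.24 | 0.04 | 0.06 |
| High unseen score | −0.64 | −0.54 | −0.42 | −0.29 |
| Low unseen score | 0.73 | 0.63 | 0.50 | 0.38 |

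Dividing the first row by the SD of 2 gives −0.22, −0.105 and −0.005 SD for the medians and the two models. A rerun of that row with one million children gave −0.45, −0.22 and 0.00 points.

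**5. Small samples** (n = 20, ρ 0.3 to 0.7, 20% or 40% dropout, 1,500 runs each). The available-case median change at week 8 was −0.19 to −0.95 points when high-pain children left, +0.17 to +0.95 when low-pain children left, and −0.01 to +0.02 with random dropout. Kruskal-Wallis rejected in 0.000 to 0.016 of runs with no or random dropout, against a nominal 0.05. It exceeded 0.05 (0.110 to 0.177) only with 40% dropout that depended on the unseen score.

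**6. Milder dropout** (15% to 25% leaving after week 2, log-odds rising 1 to 2 per SD of week 2 pain, equal or decaying correlations). The shift toward benefit at week 8 was 0.03 to 0.19 SD for medians, 0.02 to 0.09 SD for a three-visit model and within 0.002 SD of zero for five visits. Paired completers were off by up to 0.12 SD in the opposite direction at week 8 when correlation decayed with time.

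**7. Cost of five visits.** With an unstructured covariance and n − 1 denominator degrees of freedom, the type I error of the test across visits is P(F(p, n−p) > F₀.₉₅(p, n−1) × (n−p)/(n−1)), where p is the number of visits minus 1. For five visits (p = 4) it is 16% at n = 10 and 9% at n = 20. For three visits (p = 2) it is 7.0% and 5.9%.

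**The case against.** The strongest reply is that the plan may already contain the remedy. The mixed-model sentence lists no visits, and the indices it refers to could be the scores at all five. A reader might infer that no on-treatment score is ever analysed, but the text does not establish that. What stands is that the sentence follows directly on one naming three visits as those of the study, so a three-visit model is at least as natural a reading and the choice is left to the analyst.

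A reader might also infer that the plan deliberately analyses whoever attends, and that the result is biased toward benefit. The first is an inference from silence combined with an unpaired test. The second needs higher-pain children to leave, and the documents say nothing about who would leave. If improved children leave, the sign reverses.

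Three further points are fair:

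- A post-treatment target is legitimate, so leaving weeks 1 and 2 out of a baseline-to-exit contrast is not in itself an error.
- The endpoint is a change, and a paired completer analysis was near zero in the first two rows of the table and less biased than the five-visit model in the last two. But the plan does not specify a paired test, and completers were off when correlation decayed.
- The near-zero result for five visits is built in once dropout is made to depend on week 2.

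Nor is an inflated false-positive rate the main issue. Ignoring the pairing makes Kruskal-Wallis conservative in most settings. The damage is to the estimate.

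**Conclusion.** The point holds as a gap in the written plan. The named comparison is unpaired and uses three of five visits. The on-treatment scores have no assigned analysis, the mixed model's visits and the exit visit are undefined, and there is no missing-data rule. Dropout related to pain can then bias the estimated change, in a direction that the documents do not fix.

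Under the assumed 30% dropout driven by high recorded week 2 pain, the week 8 error is about 0.2 SD for available-case medians, 0.1 SD for a three-visit model and about 0 for a five-visit model. If dropout depends on the unseen score, five visits reduce the error only from −0.54 to −0.42 points (−0.27 to −0.21 SD). With random dropout there is essentially none. All of these sizes rest on assumed SD, correlation and dropout.

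One patient was enrolled and the methods were not applied, so no reported result is affected. The correction matters for the soundness of the plan and for any reuse of it.

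**What to change.** Replace the Kruskal-Wallis, pairwise-comparison and trend sentences together, so that no test is left orphaned or duplicated. Suggested text:

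> Scores from baseline and weeks 1, 2, 4 and 8 will be analysed in one repeated-measures mixed model with visit as a categorical factor, including every enrolled child, with Kenward-Roger degrees of freedom. The covariance will be unstructured, or [named simpler structure] if that model does not converge. Study exit is the [week 4 or week 8] visit. The primary result is the estimated change from baseline to that visit with its 95% CI. Changes at weeks 1 and 2 are reported as on-treatment response, and medians at all five visits are descriptive. A sensitivity analysis will assess dropout that depends on unobserved scores. The same model applies to the secondary endpoints.

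The sponsor must fill both brackets before any data are seen. The cost is wording only, because all five visits are already scheduled. The downside is that five visits in few children may not support an unstructured covariance, and without a small-sample correction the error rate is inflated (16% at n = 10). That is why the fallback structure and the degrees-of-freedom method need to be named in advance.
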